## Adverse Events

An adverse event is any untoward medical occurrence in a participant, whether or not is is causally related to the study. An adverse event can therefore be any unfavorable and unintended sign (including an abnormal laboratory finding, for example), symptom or disease temporally associated with the study.

Adverse events will be recorded on the appropriate case report forms and source documents. The investigator and/or trained staff member will evaluate all adverse events as to their severity and relation to the test article. The severity of adverse events will be graded as follows:

Mild: Awareness of a sign or symptom but easily tolerated.

Moderate: Discomfort sufficient to cause interference with usual activity or to affect clinical status.

Severe: Incapacitating with inability to do usual activity or to significantly affect clinical status.

Life Threatening: The participant was at immediate risk of death from the adverse event as it occurred.

The Investigator will also assess the relationship of any adverse event to study, based upon available information, using the following guidelines:

0 = Unlikely: No temporal association, or the cause of the event has been identified. 1 = Possible: Temporal association, but other etiologies are likely to be the cause; however, involvement of the study procedures cannot be excluded.

2 = Probable: Temporal association, other etiologies are possible, but not likely.

A *serious adverse event* is any experience that results in any of the following outcomes: death, is life threatening, results in inpatient hospitalization or prolongation of hospitalization, a persistent or significant disability/incapacity.

Important medical events that may not result in death, be life-threatening, or require hospitalization may be considered a serious adverse event when, based upon appropriate medical judgment, they may jeopardize the patient or participant and may require medical or surgical intervention to prevent one of the outcomes listed in this definition.

Side effects associated with tDCS according to the most recent data available (Brunoni, Fregni, & Pagano, 2011; Nitsche et al., 2008; Antal et al, 2007; Moliadze, Antal, & Paulus, 2010; Brignani, Ruzzoli, Mauri, & Miniussi, 2013) are:

Sensations reported by subjects under the electrodes: (These sensations can sometimes continue throughout and for a brief period following completion of the tDCS but usually resolve shortly after the initiation of tDCS)

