
Mild tingling (20-70%)

Light itching (30-40%)

Slight burning (10-22%) Discomfort or mild pain (10-18%)

Other effects that can occur both during and after tDCS include: Skin redness (20%)

Mild fatigue (15%)

Headache (10-15%)

Difficulties in concentration (11%)

Additionally the following rare side effects have been described: Nausea (<1%)

Nervousness (<1%)

Although it has never been reported in tDCS, seizures are a theoretical risk. Individuals with a history of seizures and/or a diagnosis of epilepsy will therefore be excluded from this study. EEG has not associated adverse events and is considered safe and painless.

All adverse events, Serious Adverse Events and Unanticipated Problems will be reported to the Advarra IRB according to its policies.

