Wks 1-4, D 7, 14, 21, and 28	Weekly assessments	Participants with MDD only Week 1-4 Assessment completion (Day 7, 14,21, and 28); depression symptoms and quality of life assessments	Study research assistant	30 minutes	Phone
Home tDCS administration Treatment taper period – weeks 5-8 Participant ratings of suicidality will be completed each day, and responses will be monitored and immediately be reviewed in real time by the study RA and study psychiatrist. Any changes from baseline will result in an immediate contact to the participant by the study psychiatrist.					
Wk 5, D 30,32,34	Home-based tDCS Total of 3 sessions, one every other day over a 6 day period.	The caregiver-administrator will administer the in-home tDCS session with remote staff monitoring and video conferencing if necessary Daily diary	Study research assistant	1 hour	Participant's Home
Wk 6-7, D 37,40, 43	Home-based tDCS Total of 3 sessions, one every third day over a 9 day period	The caregiver-administrator will administer the in-home tDCS session with remote staff monitoring and video conferencing if necessary Daily diary	Study research assistant	1 hour	Participant's Home
Wk 8 D 47,51, 55	Home-based tDCS Total of 3 sessions, one every fourth day over a 12 day	The caregiver-administrator will administer the in-home tDCS session with remote staff monitoring and video conferencing if necessary Daily diary	Study research assistant	1 hour	Participant's Home

	period				
Wks 5-8 D35, 42, 49, 56	Weekly assessments	Participants with MDD only Weeks 5-8 Assessment completion (Day 35, 42,49, and 56); depression symptoms and quality of life assessments	Study research assistant	30 minutes	Phone
Home tDCS administration completed after Week 8, Day 55 session. Return of Home tDCS equipment to research team in the provided shipping materials and label.					
Four week follow-up period – weeks 9-12					
Wks 9- 12 D57-84	Four week follow-up period	Participants with MDD only The study research assistant will maintain weekly contact with the participant over the 4 week follow-up period	Study research assistant	20 minutes	Phone
Week 12, Day 84	Final study assessment	Both participants: Final assessment completion, depression symptoms, quality of life assessments, cognitive assessment	Study research assistant	1 hour	Phone
End of study: Results sent to participant with MDD and treating psychiatrist					

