## **Stimulation Stopping criteria**

Subject stimulation will be stopped if any of the following occur during the 8-week treatment period:

- Clinician impression of substantial worsening of medical condition
- If the study subject misses more than 10 stimulation visits.

Study subjects will be withdrawn from the study for the following:

- If the study subject is not compliant with the study procedures as determined by the investigator.
- If, in the investigator's opinion, it is not safe for the study subject to continue with participation in the study.
- If the study subject is withdrawn from the study, the subjects treating psychiatrist will be notified so that arrangements can be made for continued treatment of his/her MDD.
- The study team will be notified by email immediately if the subject reports any adverse events during any tDCS stimulation session, and immediate follow up will occur.
- Any adverse events that take place during testing will be reported to the PI ([name]) and recorded in the database. Drs. [name], [name] and [name] will have primary responsibility for monitoring participant safety in the trial. The investigators will be responsible for reviewing each adverse event in a timely fashion and preparing a summary report for submission to the IRB.

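### The stopping section routes only adverse events arising during sessions or testing, and no scheduled contact specifies an adverse-event question, so events between sessions and in follow-up may be under-ascertained

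*Combined protocol and SAP*

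**What the plan says.** All references are to the combined protocol and SAP.

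**The general rule (Adverse Events).** The definition has no session limit: "An adverse event is any untoward medical occurrence in a participant", extending to any unfavourable sign, "symptom or disease temporally associated with the study". On recording: "Adverse events will be recorded on the appropriate case report forms and source documents". The same section sends all adverse events to the IRB. Its list of known side effects has an entry that reads "Other effects that can occur both during and after tDCS include: Skin redness (20"%) and continues with mild fatigue (15%), headache (10-15%) and difficulty concentrating (11%).

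**The operational rule (Stimulation Stopping criteria).** The team is to be "notified by email immediately if the subject reports any adverse events during any tDCS stimulation session". The next item reads "Any adverse events that take place during testing will be reported to the PI" and adds entry in the database. What counts as testing is not defined.

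**The schedule (Visits table).** Weekly calls on Days 7 to 56 list depression symptoms and quality of life. For weeks 9-12: "The study research assistant will maintain weekly contact with the participant over the 4 week follow-up period", with no content given. Day 84 lists depression, quality of life and cognition. The daily diary is entered on session rows only. Suicidality is rated daily through weeks 1-8. The equipment is returned after the Day 55 session.

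**The measure (Statistical Methods and Analysis).** Feasibility, tolerability and safety are to be judged from the number of aborted sessions, with the CogState battery as an additional safety outcome.

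**The form (list of assessments and forms).** A tDCS Side Effects Questionnaire is listed, but the visit table does not schedule it.

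**The concern.** The two sections do not describe the same set of events. A headache that begins in the evening after a session, or a problem that appears in week 10, is an adverse event under the Adverse Events section. Neither route in the stopping section mentions it, and no scheduled contact is specified as asking about it.

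The plan itself gives reasons to expect events at such times. It says that several effects occur after stimulation as well as during it, and its section on tDCS and depression says that the antidepressant effect may go on developing after the course ends.

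Safety is one of the things the study sets out to demonstrate. If events outside sessions are collected only passively, the error runs one way, towards fewer recorded events. Their timing relative to stimulation could not be described either. A later randomised trial, which this study is meant to prepare, would inherit that safety profile.

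**Working it through.** **Step 1. Compare the rules.**

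| Question | Adverse Events section | Stimulation Stopping criteria |
|---|---|---|
| Which events? | Any, if temporally associated with the study | Those reported during a session (email alert); those during testing (principal investigator, database) |
| Where do they go? | Case report forms, source documents, IRB | Study team, principal investigator, database |
| When and how is the participant asked? | Not stated | Not stated |

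The second column is narrower than the first, and neither says how events are elicited.

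**Step 2. Can the stated measure see later events?** An event that starts after a session has finished cannot cause that session to be aborted. The count of aborted sessions therefore carries no direct information on such events. The visit table places cognitive assessment at Visit 1 and Day 84 only.

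**Step 3. Count the days without a session.** Inputs are from the Visits table.

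- Session days: Days 1-28 (28), then 30, 32, 34, 37, 40, 43, 47, 51 and 55 (9). Total 28 + 9 = 37, which agrees with the 28 daily and 9 taper sessions in the text.
- Days 1-56: 56 − 37 = 19 days without a session, and 19/56 = 34%. All 19 fall in Days 29-56.
- Days 57-84: 28 of 28 without a session.
- Days 1-84: 19 + 28 = 47, and 47/84 = 56%.

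The text says the taper runs to day 60, while the table ends it on Day 55. With 37 sessions on separate days, the total of 47 is the same either way.

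**Step 4. Allow for the contact that does exist.**

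- In Days 1-28 there is a session every day. In the taper, consecutive sessions are at most 4 days apart. An effect that starts after one session can be mentioned at a later one.
- The daily suicidality rating covers Days 1-56.
- Assume that the four weekly follow-up contacts fall on Days 63, 70, 77 and 84 (the table gives only Day 84). The days with no session, no daily rating and no weekly contact are then 28 − 4 = 24, and 24/84 = 29%. All are in follow-up.

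**Step 5. What would an added question cover?** Adding the weekly contact days that are not session days (35, 42, 49, 56 and the four assumed follow-up days) leaves 84 − 37 − 8 = 39 days (46%) with no same-day contact. A question that asks about the whole period since the last contact closes that gap, because successive weekly recall periods span all 84 days.

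**Step 6. Number of events missed.** This would need the share of events that start outside sessions and the share of those never mentioned later. The documents give neither, so it cannot be computed.

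**The case against.** The strongest reply is that adverse events are covered study-wide. The Adverse Events section defines, grades and records them without a session limit and sends all of them to the IRB. The Risks section provides for triage of any participant with an adverse event. The stopping section itself ends by making investigators responsible for reviewing each event. Read this way, the email sentence describes only an in-session alert.

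There is also capture that a quick reading misses. The home tablet is used to record side effects, suicidality is rated daily for eight weeks with real-time review, sessions are frequent through Day 55, and the cognitive battery is a safety outcome. The diary, the questionnaire and the training manual are named but not reproduced, so they may ask the right questions.

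Most of this stands, and it rules out two stronger readings.

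- A reader might infer that safety is under-counted on the 56% of days without a session. The day count is right, but a day without a session is not a day on which events go unrecorded. Events can be volunteered, or recalled at a later session or call, and 28 of the 47 days are follow-up without stimulation.
- A reader might apply the listed side-effect rates to the 50 participants and estimate the events lost. The documents do not give the proportion starting after a session or say whether the rates are per participant or per session.

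The reply does not answer three things. The general rule says what counts and where it is written, not when anyone asks. The suicidality rating covers one domain and is stated only for weeks 1-8. The tablet route closes when the equipment is returned. Silence about call content does not show that the calls omit adverse events, but the plan does not specify that they include them.

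**Conclusion.** The concern holds as an inconsistency and a gap in specification. The routes to the team, the principal investigator and the database are worded for events during sessions or testing, whereas the plan's definition covers all events during the study. No scheduled contact specifies a general adverse-event inquiry, the side-effects form has no time point, and the stated safety measure cannot register events that start after a session.

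Under-ascertainment is therefore possible, chiefly in the 28 follow-up days after the device is returned. It is possible to a lesser degree on the 19 of 56 treatment and taper days (34%) without a session, where later sessions and daily ratings offer some chance of capture. Any such bias would be towards fewer recorded events; its size is not estimable from the documents.

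This rests on the visit table as printed and on the unseen forms not already supplying a scheduled inquiry. If they do, the remedy reduces to stating that in the protocol and reconciling the two sections. The point deserves correction because safety is in the primary objective, but it does not show that adverse-event reporting as a whole is confined to sessions.

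**What to change.** 1. Reconcile the stopping section with the Adverse Events section, so that every adverse event from consent to Day 84, in or between sessions, goes to the principal investigator and into the database. Define or remove the term testing.
2. Add an open question about any new problem since the last contact, together with the existing tDCS Side Effects Questionnaire, to the weekly calls on Days 7-56, the weekly calls in weeks 9-12 and Day 84. Show both in the visit table.
3. Record the onset of each event relative to the most recent session.
4. In the analysis section, report these data alongside aborted sessions as the safety result.

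This uses contacts, staff and a form already in the plan and changes data collection only. The costs are slightly longer calls and higher reported event rates than passive collection would give. The higher rates should be borne in mind when comparing with studies that collected events differently.

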## Data storage and confidentiality

Data will be kept on a secure, password protected HSL server in a REDCap Database. Only study members at the HSL site will have access to the HSL REDCap database. All hard copy forms will be kept in a locked filing cabinet that only study members will be able to access. All policies and procedures of Hebrew Senior Life with regard to data storage will be followed.

Data collected will be stripped of identifiers. Data will be assigned a code number and no personal identifying information will be associated with study data in any format, including electronically. Only the investigators will know information about a particular subject. Identifying information about a subject will be stored in locked computer files and cabinets and will not be used during the discussion, presentation, or publication of any research data.

Results of the study will be shared with the participant's psychiatrist if the participant has given study staff permission to do so.

List of Assessments and forms:

[Sociodemographic form\\_2 8619.docx](#)

[Medical History Questionnaire\\_1 92718.docx](#)

[Medication Review Form\\_1 92818.docx](#)

[Q\\_LES\\_Q\\_SF.docx](#)

[QIDS\\_SR.pdf](#)

[Suicide Risk Assessment Protocol.pdf](#)

[tDCS Eligibility Questionnaire\\_41220.docx](#)

[001\\_Coverletter-Depression.docx](#)

[002\\_HOME\\_tDCS\\_MDD\\_STUDY\\_04\\_07\\_2020\\_v1.0.docx](#)

[003\\_Annex I- Safety Analysis of tDCS in Craniotomies.docx](#)

[004\\_Annex II-Home based tDCS for MDD Training Manual.docx](#)

[005\\_Annex III-Caregiver tDCS Competency Checklist.docx](#)

[006\\_Annex IV-SPR0157\\_IDLPFC\\_DepressionHome.pdf](#)

[Assessment of Understanding Protocol\\_mdd.docx](#)

[tDCS Side Effects Questionnaire\\_mdd.docx](#)

[FDA IDE approval letter G160208-S003.Letter.NEWS.APPR \(002\).pdf](#)

[Evaluation Form Home based tDCS in MDD\\_Caregiver-administrator.docx](#)

[Revised CPQ\\_v1.docx](#)

[Proxy and Medical care Info.792019.docx](#)

[Evaluation Form Home based tDCS in MDD\\_v2PMDD.docx](#)

[PhoneScreenQuestionnaire\\_Caregiver-administrator\\_clean.docx](#)

[PhoneScreenQuestionnaire\\_PMDD\\_v2\\_5420.docx](#)

[tDCS Eligibility Questionnaire\\_41220.docx](#)

[Home based tDCS MDD Training Manual v5 5120.docx](#)

[MADRS.pdf](#)

[Evaluation Form Home based tDCS in MDD\\_v2PMDD.docx](#)

[Caregiver-administrator tDCS Competency Checklist\\_1 5120](#)
